
 Any participant that receives administration of an alternative or additional antibacterial therapy before the Follow-up Visit will be assigned a microbiological outcome of “unable to determine” and a response of “microbiological failure.” Participants considered microbiological failures at the TOC Visit will also be considered microbiological failures at the Follow-up Visit. 		
A quantitative urine culture taken at the Follow-up Visit shows reduction of the qualifying bacterial uropathogen recovered at Baseline to $<10^3$ CFU/mL	Sustained microbiological eradication	Microbiological success
A quantitative urine culture taken at the Follow-up Visit shows that the qualifying bacterial uropathogen recovered at Baseline grows $\geq 10^3$ CFU/mL	Microbiological recurrence	Microbiological failure
A determination of the baseline qualifying bacterial uropathogen microbiological response cannot be made (e.g., no urine culture taken, sample lost, etc.)	Unable to determine	Microbiological failure
A new qualifying bacterial uropathogen, not identified at Baseline, is documented by quantitative urine culture at the Follow-up Visit in a participant who is a clinical failure	New infection	Microbiological failure
A new qualifying bacterial uropathogen, not identified at Baseline, is documented by quantitative urine culture at the Follow-up Visit in a participant who is a clinical success	Colonization	Microbiological success

CFU=colony-forming units; TOC=Test-of-Cure.

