
 Any participant that receives administration of an alternative or additional antibacterial therapy before the TOC Visit will be assigned a microbiological outcome of “unable to determine” and a response of “microbiological failure”. Participants considered microbiological failures at the TOC Visit will also be considered microbiological failures at the Follow-up Visit. 		

 A quantitative urine culture taken at the TOC Visit shows reduction of the qualifying bacterial uropathogen recovered at Baseline to <10³ CFU/mL 	
 Microbiological eradication 	
 Microbiological success

 A quantitative urine culture taken at the TOC Visit shows that the qualifying bacterial uropathogen recovered at Baseline, and which was also shown to persist at the On-Therapy Visit, grows ≥10³ CFU/mL 	
 Microbiological persistence 	
 Microbiological failure

 A quantitative urine culture taken at the TOC Visit shows that the qualifying bacterial uropathogen recovered at Baseline, and which was also shown to be eradicated at the On-Therapy Visit, grows ≥10³ CFU/mL 	
 Microbiological recurrence 	
 Microbiological failure

 A determination of the baseline qualifying bacterial uropathogen microbiological response cannot be made (e.g., no urine culture taken, sample lost, etc.) 	
 Unable to determine 	
 Microbiological failure

 A new qualifying bacterial uropathogen, not identified at Baseline, is documented by quantitative urine culture at the TOC Visit in a participant who is a sponsor-determined clinical failure 	
 New infection 	
 Microbiological failure

 A new qualifying bacterial uropathogen, not identified at Baseline, is documented by quantitative urine culture at the TOC Visit in a participant who is a sponsor-determined clinical success 	
 Colonization 	
 Microbiological success

CFU=colony-forming units; TOC=Test-of-Cure.

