Table 6 Microbiological Outcome and Response by Qualifying Uropathogen at the Follow-Up Visit

Defining Criteria	Outcome	Response

 Any participant that receives administration of an alternative or additional antibacterial therapy before the Follow-up Visit will be assigned a microbiological outcome of “unable to determine” and a response of “microbiological failure”. Participants considered microbiological failures at the TOC Visit will also be considered microbiological failures at the Follow-up Visit. 		

 A quantitative urine culture taken at the Follow-up Visit shows reduction of the qualifying bacterial uropathogen recovered at Baseline to $<10^3$ CFU/mL 	
 Sustained microbiological eradication 	
 Microbiological success

 A quantitative urine culture taken at the Follow-up Visit shows that the qualifying bacterial uropathogen recovered at Baseline grows $\geq 10^3$ CFU/mL 	
 Microbiological recurrence 	
 Microbiological failure

 A determination of the baseline qualifying bacterial uropathogen microbiological response cannot be made (e.g., no urine culture taken, sample lost, etc.) 	
 Unable to determine 	
 Microbiological failure

 A new qualifying bacterial uropathogen, not identified at Baseline, is documented by quantitative urine culture at the Follow-up Visit in a participant who is a sponsor-determined clinical failure 	
 New infection 	
 Microbiological failure

 A new qualifying bacterial uropathogen, not identified at Baseline, is documented by quantitative urine culture at the Follow-up Visit in a participant who is a sponsor-determined clinical success 	
 Colonization 	
 Microbiological success

CFU=colony-forming units; TOC=Test-of-Cure.

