
 • Refusal to consent to a clinical examination or failure to attend the On-Therapy visit (Days 2 through 5 only) 	
 • Unable to Determine 	
 • Not applicable
Test-of-Cure Visit		

 • Resolution of signs and symptoms of acute cystitis (total cumulative score is zero) present at Baseline (and no new signs or symptoms) and no use of other antimicrobial therapy 	
 • Clinical success 	
 • Success

 • Persistence of signs and symptoms of infection (total cumulative score is >0), reappearance of signs and symptoms, or use of other antimicrobial therapy for the current infection 	
 • Clinical failure 	
 • Failure

 • Refusal to consent to a clinical examination or failed to attend the TOC Visit 	
 • Unable to determine 	
 • Failure

Follow-up Visit		

 Resolution of signs and symptoms of acute cystitis demonstrated at the TOC Visit persist at the Follow-up Visit (total cumulative score is zero) (and no new signs and symptoms) and no use of other antimicrobial therapy 	
 Sustained clinical success 	
 Success

 Resolution of signs and symptoms of acute cystitis at the Follow-up Visit (total cumulative score is zero) and no use of other antimicrobial therapy, but lack of clinical success at the TOC Visit 	
 Delayed clinical success 	
 Failure

 Persistence of signs and symptoms of infection (total cumulative score is >0), reappearance of signs and symptoms, or use of other antimicrobial therapy for the current infection 	
 Clinical failure 	
 Failure

 Signs and symptoms of acute cystitis absent at the TOC Visit re-occur at the Follow-up Visit and no use of other antimicrobial therapy 	
 Clinical recurrence 	
 Failure

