
 Refusal to consent to a clinical examination or failed to attend the Follow-up Visit 	
 Unable to determine 	
 Failure

TOC=Test-of-Cure.

Table 8 Clinical Cure

Defining Criteria	Clinical Cure (Yes/No)
On-Therapy visit (Days 2 through 5 only), Test-of-Cure visit, and Follow-up visit	

 Complete resolution of signs and symptoms of acute cystitis present at Baseline, with no new signs and symptoms, and no use of other antimicrobial therapy. Clinical Cure at Follow-up must also meet Clinical Cure at Test-of-Cure in addition to above criteria. 	
 Yes

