12.9.6. Efficacy Figures

Efficacy: Tables					
No.	Population	IDSL / Example Shell	Title	Programming Notes	Deliverable
2.1.	Micro-ITT	EFF_F1	Percent of Clinical Cure and Microbiological Eradication Over Time by Uropathogen Isolated at Baseline		DS, SAC
2.2.	Micro-ITT	EFF_F2	Quantitative Bacterial Counts (CFU/mL) by Qualifying Baseline Uropathogen Over Time		DS, SAC
2.3.	Micro-ITT	EFF_F3	Individual Clinical Symptom Score and Boxplot of Total Score Over Time		DS, SAC

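### The Follow-up outcome of sustained microbiological eradication has no Test-of-Cure condition, so late clearance can be counted as sustained although its response is correctly a failure

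*SAP*

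**What the plan says.** Microbiological outcome and response are assigned by a programmed algorithm. At Follow-up, SAP Table 6 and protocol Table 5 give the outcome "Sustained microbiological eradication", paired with response success, on one condition: "A quantitative urine culture taken at the Follow-up Visit shows reduction of the qualifying bacterial uropathogen recovered at Baseline to" below 10³ CFU/mL.

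Two header rules in SAP Table 6 sit above the rows:

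- **Other antibacterial use.** The rule opens: "Any participant that receives administration of an alternative or additional antibacterial therapy before the Follow-up Visit will be assigned a microbiological outcome of". The outcome it then names is *unable to determine*, and it sets the response to failure, so it resets both columns.
- **Carry-forward.** "Participants considered microbiological failures at the TOC Visit will also be considered microbiological failures at the Follow-up Visit". This rule uses the vocabulary of the Response column and names no outcome.

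SAP Table 5 shows who is a microbiological failure at TOC. The group includes persistence, recurrence, and the case where "A determination of the baseline qualifying bacterial uropathogen microbiological response cannot be made (e.g., no urine culture taken, sample lost, etc".

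The clinical tables treat the same situation differently. SAP Table 7 has a separate outcome, *delayed clinical success*, for resolution at Follow-up "but lack of clinical success at the TOC Visit", with response failure. SAP Table 8 adds: "Clinical Cure at Follow-up must also meet Clinical Cure at Test-of-Cure".

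Two planned micro-ITT displays use these results. Table 2.1 tabulates microbiological outcome and response by visit. Figure 2.1 is titled "Percent of Clinical Cure and Microbiological Eradication Over Time by Uropathogen Isolated at Baseline".

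**The concern.** The word sustained says that an earlier state has held. A pathogen that was growing at TOC, or was not cultured there, cannot be shown by a single later culture to have stayed eradicated. Under the written rule it is still reported that way. The Table 6 row pairs the label with success and the header forces failure, so the participant's record reads as a sustained eradication that failed. Because the outcome is programmed, nobody adjudicates that record.

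Microbiological outcome at Follow-up is a listed exploratory endpoint, and Follow-up is the visit at which relapse is assessed. Late clearance and sustained eradication are different findings there, and Table 2.1 would merge them. In Figure 2.1 the clinical cure point at Follow-up requires cure at TOC. The eradication point would have no matching condition if it is built from this outcome.

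**Working it through.** No figure in the plan depends on this rule, so there is none to reproduce. The check applies SAP Tables 5 and 6 literally.

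**Inputs.** TOC culture of the baseline pathogen: <10³, ≥10³ or none (SAP Table 5). Other antibacterial before TOC: yes or no (headers of SAP Tables 5 and 6). Follow-up culture: <10³, ≥10³ or none (SAP Table 6). Enrolment: 25 to 30 (SAP Section 2.3). Micro-ITT size: not stated.

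**Step 1: enumerate.** 3 × 2 × 3 = 18 combinations. With another antibacterial, all 3 × 3 = 9 give unable to determine and failure at Follow-up. An antibacterial started between TOC and Follow-up falls under the same Table 6 header, so it adds no affected case. The 9 combinations without one are shown below as outcome / response at Follow-up.

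| TOC culture (TOC response) | Follow-up <10³ | Follow-up ≥10³ | No Follow-up culture |
|---|---|---|---|
| <10³ (success) | sustained / success | recurrence / failure | unable to determine / failure |
| ≥10³ (failure) | **sustained / failure** | recurrence / failure | unable to determine / failure |
| none (failure) | **sustained / failure** | recurrence / failure | unable to determine / failure |

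**Step 2: check the response.** TOC is a failure in 9 + 6 = 15 of the 18 combinations, and in all 15 the Follow-up response is failure. The only Follow-up success is <10³ at both visits with no other antibacterial.

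**Step 3: apply a TOC condition.** If the sustained label also requires eradication at TOC, exactly the two bold cells lose it. Their response stays failure.

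**Step 4: size.** With k affected participants in a row of denominator n, the eradication percentage is overstated by 100 × k/n points. For k = 1:

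| Assumed n | Shift (points) |
|---|---|
| 30 | 100/30 = 3.3 |
| 20 | 100/20 = 5.0 |
| 10 | 100/10 = 10.0 |
| 5 | 100/5 = 20.0 |

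Enrolment makes 30 about the most participants there could be. The smaller values cover a reduced micro-ITT population or a single pathogen group, since both displays are by uropathogen.

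**Step 5: a related label.** In the column for Follow-up ≥10³, the outcome is recurrence even where the pathogen was also growing at TOC. The response is right, but recurrence has no TOC condition either.

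**The case against.** The strongest reply is that the table already protects what matters. Header rules are general overrides, their precedence for the response is clear, and no success rate changes. The Clopper-Pearson interval in SAP Section 9.1.1.1 is for microbiological response, and therapeutic response is built from microbiological success, so neither moves. Efficacy is exploratory in a study with no formal hypothesis test. All of this stands. It limits the point to an outcome label but does not correct the label: the antibacterial rule names a replacement outcome, the carry-forward rule names none, and no other Table 6 outcome fits these women.

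A second reply is that the clinical change had a different motive. SAP Section 2.1 explains the sponsor-determined outcome by the risk that an investigator would call a woman with no TOC record but no symptoms at Follow-up a success. Microbiological outcome involves no such judgement. That is fair, and the clinical tables do not prove an oversight here. They do show that the SAP separates late from sustained resolution where it deals with the question.

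Third, a woman with a new infection at TOC can have her baseline pathogen below 10³ CFU/mL at both visits and still be a failure. She would remain sustained with response failure after the fix. For that pathogen the label is true, so this is not the same error.

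A reader might also infer more than the documents support:

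- **That the label rests on the Follow-up culture alone.** It does not, because other antibacterial use moves the participant to unable to determine. Under protocol Section 5.1, women with continuing symptoms are assessed and treated at the investigator's judgement, so some TOC persisters leave the affected group this way.
- **That the two curves in Figure 2.1 cannot be compared.** Days 2 to 5 and TOC are visit-specific for both. Only the Follow-up point is in question, and only if it plots the Table 6 outcome. The SAP does not say so, and the figure shell is not in the documents. Section 9.1.1.4 also describes a similar plot with clinical success instead of clinical cure.
- **That an overall percentage overstatement can be stated.** It would need the share of women not shown eradicated at TOC and the share of those below 10³ CFU/mL at Follow-up. The documents give neither.

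**Conclusion.** The point holds for the outcome label. As written, a participant with growth or no culture at TOC, no other antibacterial, and less than 10³ CFU/mL at Follow-up is reported as a sustained eradication. If such a participant occurs, Table 2.1 overstates sustained eradication at Follow-up by 1/n for each one. The Follow-up point of Figure 2.1 shifts by the same amount if it uses this outcome. That is 3.3 points at n = 30 and 10 points at n = 10, both assumed denominators. The number affected is unknown and may be zero.

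It would be wrong to conclude that microbiological or therapeutic success is inflated, because the carry-forward rule makes these women failures. No primary or secondary result is touched. The correction is still worth making before database freeze, because a later relabelling would be post hoc.

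**What to change.** In SAP Table 6, with the departure from protocol Table 5 recorded in SAP Section 2.1:

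1. Define *sustained microbiological eradication* as below 10³ CFU/mL at Follow-up **and** eradication of that pathogen at TOC.
2. Add *delayed microbiological eradication*: below 10³ CFU/mL at Follow-up without eradication at TOC, with response microbiological failure. This parallels *delayed clinical success* in Table 7.
3. For consistency, limit *recurrence* at Follow-up to pathogens eradicated at TOC, and label growth at both visits *persistence*. Name an outcome for growth at Follow-up with no TOC culture. The response is failure in each case, as now.
4. State that the Follow-up point of Figure 2.1 counts only sustained eradication.

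The cost is a few lines of table wording and the matching programming conditions, with no new data. The downside is that the reported Follow-up eradication percentage may fall slightly.

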9.1.1.2. Susceptibility

- Results and interpretations of susceptibility testing for all uropathogens against gepotidacin and other antimicrobials will be summarized by uropathogen, visit, and antimicrobials tested. For summaries, a participant will be counted multiple times under an uropathogen category if multiple uropathogens within that uropathogen category are isolated at baseline for the participant.
- The overall frequency distribution of minimum inhibitory concentrations (MICs) and the minimum, maximum, median (MIC₅₀), and 90th percentile (MIC₉₀) MIC will be presented. Percent susceptibility (susceptible, intermediate, or resistant) will be summarized where available.
- Reduction in susceptibility to gepotidacin will be evaluated by comparing the baseline gepotidacin MIC value for uropathogens with the value obtained post-baseline. Post-baseline uropathogens of the same species and from the same participant with a confirmed ≥ 4 -fold increase in gepotidacin MIC are considered to have developed a reduction in susceptibility to gepotidacin.

- The number and percentage of participants who demonstrate a reduction in susceptibility to GSK 2140944 will be summarized by visit and uropathogen. A participant will be counted multiple times under an uropathogen category if multiple uropathogens within that uropathogen category are isolated at baseline for the participant.

9.1.1.3. Clinical Outcome and Response

- Clinical signs and symptoms of acute cystitis will be recorded by site staff based on participant interview using the scoring system.
- The clinical signs and symptoms include at least dysuria, frequency, urgency, and lower abdominal or suprapubic pain. The clinical signs and symptoms will be scored from 0 to 3.
- At Baseline, the participant must present with at least 2 signs and symptoms and have a total cumulative symptom score ≥ 2 . At TOC, success is recorded as normal presentation of signs and symptoms with a total cumulative symptom score of zero and no new signs and symptoms of the infection under study.
- The investigator will determine the clinical outcome by comparing the signs and symptoms of acute cystitis at the On-Therapy (Days 2 through 5 only), TOC, and Follow-up Visits to those present at Baseline. The clinical response based on investigator-determined clinical outcome will be programmatically derived using the criteria in [Table 7](#).
- The sponsor-determined clinical outcome and response will be programmatically determined by comparing the scores of the signs and symptoms of acute cystitis at the On-Therapy (Days 2 through 5 only), TOC, and Follow-up Visits to those present at Baseline as shown in [Table 7](#).
- Participants who withdraw from the study prior to TOC or Follow-Up Visits will be considered not achieving success as the clinical response at TOC or Follow-Up Visits. The investigator- and sponsor-determined clinical response and outcome at Early Termination visit will only be listed.
- Clinical response (success or failure) will be determined at TOC or Follow-Up visits for each participant. A “success” clinical response is defined as if the clinical outcome for all qualifying uropathogens is “clinical success” for the visit, otherwise a “failure” clinical response will be assigned.
- Clinical cure is defined in [Table 8](#) and will be programmatically derived at the On Therapy (Days 2 through 5), TOC, and Follow-up Visits. If a participant does not meet clinical cure at TOC visit, the participant will not be considered as clinical cure at Follow-up visit.
- The investigator- and sponsor-determined clinical outcome and response will be summarized for qualifying uropathogens isolated at baseline at the On-therapy, TOC, and Follow-up visits using counts and percentages. A participant will be counted multiple times under an uropathogen category if multiple qualifying uropathogens within that uropathogen category are isolated at baseline for the participant. In addition, participant level of clinical outcome will be summarized in the same table. The 95% Clopper-Pearson CI will be presented for the proportion clinical response at each visit.

- Clinical cure will be summarized for qualifying uropathogens isolated at baseline at the On-therapy, TOC, and Follow-up visits using counts and percentages.
A participant will be counted multiple times under an uropathogen category if multiple qualifying uropathogens within that uropathogen category are isolated at baseline for the participant. The 95% Clopper-Pearson CI will be presented for the proportion clinical cure at each visit.
- Percent of clinical cure and microbiological eradication over time will be plotted.
A participant with multiple qualifying uropathogens within an uropathogen category will be counted multiple times.
- The mean clinical symptom scores and boxplots of total score over time will be overlaid within one figure for the ITT population.

Table 7 Sponsor-Determined Clinical Outcome and Response

Defining Criteria	Outcome	Response
On-Therapy visit (Days 2 through 5 only)		

 • Resolution of or improvement in signs and symptoms of acute cystitis present at Baseline (and no new signs and symptoms) • Improvement is based on investigator-evaluated score and is defined as no increase of scores in each sign and symptom of acute cystitis present at Baseline and no new signs and symptoms of acute cystitis and no use of other antimicrobial therapy for the current infection 	
 • Clinical success 	
 • Not applicable

 • Increase of scores in any of signs and symptoms of acute cystitis present at Baseline or new signs and symptoms of acute cystitis or use of other antimicrobial therapy for the current infection 	
 • Clinical failure 	
 • Not applicable

 • Refusal to consent to a clinical examination or failure to attend the On-Therapy visit (Days 2 through 5 only) 	
 • Unable to Determine 	
 • Not applicable
Test-of-Cure Visit		

 • Resolution of signs and symptoms of acute cystitis (total cumulative score is zero) present at Baseline (and no new signs or symptoms) and no use of other antimicrobial therapy 	
 • Clinical success 	
 • Success

 • Persistence of signs and symptoms of infection (total cumulative score is >0), reappearance of signs and symptoms, or use of other antimicrobial therapy for the current infection 	
 • Clinical failure 	
 • Failure

 • Refusal to consent to a clinical examination or failed to attend the TOC Visit 	
 • Unable to determine 	
 • Failure

Follow-up Visit		

 Resolution of signs and symptoms of acute cystitis demonstrated at the TOC Visit persist at the Follow-up Visit (total cumulative score is zero) (and no new signs and symptoms) and no use of other antimicrobial therapy 	
 Sustained clinical success 	
 Success

 Resolution of signs and symptoms of acute cystitis at the Follow-up Visit (total cumulative score is zero) and no use of other antimicrobial therapy, but lack of clinical success at the TOC Visit 	
 Delayed clinical success 	
 Failure

 Persistence of signs and symptoms of infection (total cumulative score is >0), reappearance of signs and symptoms, or use of other antimicrobial therapy for the current infection 	
 Clinical failure 	
 Failure

 Signs and symptoms of acute cystitis absent at the TOC Visit re-occur at the Follow-up Visit and no use of other antimicrobial therapy 	
 Clinical recurrence 	
 Failure

 Refusal to consent to a clinical examination or failed to attend the Follow-up Visit 	
 Unable to determine 	
 Failure

TOC=Test-of-Cure.

Table 8 Clinical Cure

Defining Criteria	Clinical Cure (Yes/No)
On-Therapy visit (Days 2 through 5 only), Test-of-Cure visit, and Follow-up visit	

 Complete resolution of signs and symptoms of acute cystitis present at Baseline, with no new signs and symptoms, and no use of other antimicrobial therapy. Clinical Cure at Follow-up must also meet Clinical Cure at Test-of-Cure in addition to above criteria. 	
 Yes

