9.1.1.4. Therapeutic Response

- A measure of overall efficacy response, success, or failure.
- A therapeutic success refers to participants who have been deemed both a ‘microbiological success’ (refer to ‘Microbiological Outcome and Response’) and a ‘clinical success’ (i.e., ‘responders’)
- All other combinations will be deemed failures for therapeutic response.
- Programmatically derived for TOC and Follow-up Visits
- Number of participants achieving therapeutic success at the TOC and Follow-up visits along with the 95% Clopper-Pearson CI will be summarized by per-participant microbiological response and clinical response by qualifying uropathogens isolated at baseline. A participant will be counted multiple times under an uropathogen category if multiple qualifying uropathogens within that uropathogen category are isolated at baseline for the participant.
- Percent of clinical success and microbiological eradication over time will be plotted.

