9.1.3. Population of Interest

The exploratory efficacy analyses will be based on the “micro-ITT” population, unless otherwise specified.

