12.9.5. Efficacy Tables

Efficacy: Tables					
No.	Population	IDSL / Example Shell	Title	Programming Notes	Deliverable
Bacteriology Assessments and Microbiological Outcome and Response					
2.1.	Micro-ITT	EFF_T1	Summary of Microbiological Outcome and Response by Visit and Qualifying Uropathogen Isolated at Baseline		DS, SAC
2.2.	Micro-ITT	EFF_T2	Summary of Urine Quantitative Bacteriology Culture Results by Qualifying Uropathogen and Visit		DS, SAC
2.3.	Micro-ITT	EFF_T3	Summary of MIC and Susceptibility Results of Qualifying Uropathogens	Summarize only qualifying uropathogens (flagged by study microbiologist and/or clinical scientist), including those no present at baseline but emerging later	DS, SAC
2.4.	Micro-ITT	EFF_T4	Distribution of MIC Results of Qualifying Uropathogens by Drug	Summarize only qualifying uropathogens (flagged by study microbiologist and/or clinical scientist), including those no present at baseline but emerging later	DS, SAC
2.5.	ITT	EFF_T5	Summary of Reduction in Susceptibility to Gepotidacin	Summarize all uropathogens regardless of counts	DS, SAC
Clinical Outcome and Response, Therapeutic Response					
2.6.	Intent-to-Treat	EFF_T6	Summary of Investigator-Determined and Sponsor-Determined Clinical Outcome and Response by Uropathogen Isolated at Baseline		DS, SAC
2.7.	Micro-ITT	EFF_T7	Summary of Therapeutic Response		DS, SAC
2.8.	ITT	EFF_T8	Summary of Clinical Symptom Score by Visit		DS, SAC

Efficacy: Tables					
No.	Population	IDSL / Example Shell	Title	Programming Notes	Deliverable
2.9.	ITT	EFF_T9	Summary of Clinical Cure by Qualifying Uropathogen Isolated at Baseline		DS, SAC

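### SAP 9.1.1.3 gives two conflicting rules for participant-level clinical response, and clinical, cure and therapeutic results are counted more than once within a uropathogen category under exact binomial intervals

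*SAP*

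**What the plan says.** **Two rules for one variable (SAP 9.1.1.3).**
- The section points to Table 7: "The clinical response based on investigator-determined clinical outcome will be programmatically derived using the criteria in" that table. The sponsor-determined outcome and response are also to be derived as Table 7 shows.
- A later bullet opens at participant level: "Clinical response (success or failure) will be determined at TOC or Follow-Up visits for each participant". It then adds that a successful "clinical response is defined as if the clinical outcome for all qualifying uropathogens is" *clinical success* for the visit, with failure otherwise.
- In the Follow-up block of Table 7, only "Sustained clinical success" maps to Success. *Delayed clinical success* maps to Failure, and the plain label *Clinical success* does not appear there.

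**Counting.**
- For clinical outcome and response, and again for clinical cure, SAP 9.1.1.3 states: "A participant will be counted multiple times under an uropathogen category if multiple qualifying uropathogens within that uropathogen category are isolated at baseline". A 95% Clopper-Pearson interval is planned for each.
- A participant-level clinical outcome summary is also planned in the same table as clinical response.
- SAP 9.1.1.4 reports "Number of participants achieving therapeutic success at the TOC and Follow-up visits along with the 95% Clopper-Pearson CI" by baseline uropathogen, with the same repeat-counting sentence.
- SAP 12.4.4 keeps two isolates of one species as separate strains when their MIC patterns differ enough.

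**Populations.**
- Protocol 10.3.3 assigns clinical outcome and response to the micro-ITT population. SAP 9.1.3 agrees by default: "The exploratory efficacy analyses will be based on the" micro-ITT population, unless otherwise specified.
- In SAP 12.9.5, Table 2.6 ("Summary of Investigator-Determined and Sponsor-Determined Clinical Outcome and Response by Uropathogen Isolated at Baseline") and Table 2.9 (clinical cure) are on ITT.
- Listing 16 shows sponsor-determined clinical response for participants outside micro-ITT as well.
- The table of changes in SAP 2.1 does not mention the use of ITT.

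**The concern.** Clinical outcome rests on symptom scores, attendance and use of other antimicrobials. None of these has a value per uropathogen. The disputed bullet reads like the participant-level microbiological rule in SAP 9.1.1.1, where requiring success for every pathogen makes sense. Here it tests something that is not defined, and it competes with a table that already gives the answer.

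The same mismatch of unit appears in the tabulations. One participant-level result is entered once per isolate, and the interval then treats the entries as independent.

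At stake are the exploratory clinical, cure and therapeutic rates. They include Follow-up therapeutic response, which serves the relapse objective.

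**Working it through.** The documents state no rate, power or precision for clinical or therapeutic response, so there is no planned figure to reproduce. The check has three parts. Sample sizes and rates below are assumptions, except that 25 to 30 participants are to be enrolled.

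**1. The bullet against Table 7.** Code the bullet as: success if the outcome equals *Clinical success* for all qualifying uropathogens, otherwise failure.

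| Visit and outcome | Table 7 | Bullet, 1 or 2 pathogens | Bullet, no pathogen (universal test) |
|---|---|---|---|
| TOC, clinical success | Success | Success | Success |
| TOC, clinical failure or unable to determine | Failure | Failure | Success |
| Follow-up, sustained clinical success | Success | **Failure** | Success |
| Follow-up, the other four outcomes | Failure | Failure | Success |

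The two rules agree at test-of-cure (TOC) for anyone with a pathogen. At Follow-up the literal bullet gives 0/n whatever the data. Suppose 14 of 20 are sustained successes: Table 7 gives 70% (95% CI 45.7 to 88.1%), and the bullet gives 0/20 (0 to 16.8%). Therapeutic success needs clinical success, so it would also be zero at Follow-up. A loose text match on the words does not help, because it would also accept *Delayed clinical success*.

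**2. ITT participants without a qualifying uropathogen.** For them, all qualifying uropathogens is an empty set. A universal test returns Success for everyone, including clinical failures. Code that requires at least one record returns Failure for everyone. Suppose, at TOC, 30 ITT participants, 10 without a pathogen, and 80% success in both groups (16 of 20 and 8 of 10):
- Table 7: (16 + 8)/30 = 24/30 = 80%
- Empty set counted as success: (16 + 10)/30 = 26/30 = 87%
- Empty set counted as failure: (16 + 0)/30 = 16/30 = 53%

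With 5 to 15 such participants among 25 or 30, and the same 80%, the two codings span 83 to 92% and 32 to 67%.

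**3. Repeat counting.** Let n participants in a category share success probability p, with m of them entered twice with the same result. With a successes among the m and b among the other n − m, the table shows (2a + b)/(n + m). Exact coverage is the sum, over a and b, of Bin(a; m, p) × Bin(b; n − m, p) wherever the Clopper-Pearson interval for (2a + b)/(n + m) contains p. The minimum is taken over p from 0.50 to 0.99.

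| n | m = 0 | m = 1 | m = 2 | m = n |
|---|---|---|---|---|
| 10 | 96.1% | 93.8% | 91.4% | 77.1% |
| 20 | 95.8% | 94.3% | 93.0% | 74.9% |

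The last column is an extreme bound. The percentage moves as well. Take 8 successes in 10 participants, 80% (44.4 to 97.5%):
- Two successes entered twice: 10/12 = 83% (51.6 to 97.9%)
- Two failures entered twice: 8/12 = 67% (34.9 to 90.1%)

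**The case against.** **On the two rules.** Other bullets in the same section send the derivation to Table 7, and the disputed bullet itself opens at participant level. Protocol 9.1.3 and SAP Table 6 use clinical success generically at Follow-up. A uniform 0% should also be conspicuous in the dry run planned in SAP 12.9.3. This stands to the extent that the Follow-up error arises only if the bullet overrides Table 7. It does not remove the conflict: the SAP never says which rule governs, and a programmer reaches the right answer only by setting the bullet aside.

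**On participants without a pathogen.** Table 7 classifies them without difficulty, and clinical cure (Table 8) does not use the bullet at all. Both statements are correct. The arbitrary answer comes from the bullet alone.

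**On repeat counting.** The convention is stated openly. It needs two qualifying uropathogens in one category in one participant, and same-species isolates count separately only with a 4-fold or greater MIC difference in two or more antibiotic classes. The documents give no expected frequency, so few participants may be affected. Clopper-Pearson is conservative: with 2 of 10 duplicated, coverage averaged over the same range of p is still 96.0%. The interval for clinical response may be meant for the participant-level summary, since its sentence directly follows that one. All this limits the size. It does not repair the rows that contain repeats, and for clinical cure and therapeutic response no participant-level row is stated.

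**On populations.** SAP 9.1.3 allows exceptions, and the symptom-resolution objective is not limited to participants with a qualifying uropathogen, so ITT is defensible. What stands is that the departure from protocol 10.3.3 is not listed as a change.

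**Conclusion.** Two defects hold as written, and both should be corrected before programming.

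1. SAP 9.1.1.3 contains conflicting rules for clinical response. The bullet, if coded in place of Table 7, fails every Follow-up success and gives an arbitrary result for ITT participants without a qualifying uropathogen in Table 2.6 and Listing 16.
2. Clinical response, clinical cure and therapeutic response are counted repeatedly within uropathogen categories. In any row with repeats, the figure is not a proportion of participants, and the exact interval loses its guaranteed 95% coverage. Illustratively, the minimum is 91.4% with 2 of 10 duplicated and 93.0% with 2 of 20, against about 96% with none. These figures rest on assumed n and m.

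A reader might infer more than the documents support:
- *That the plan produces a 0% Follow-up rate.* It does so only if the bullet replaces Table 7.
- *That therapeutic response is derived per uropathogen.* SAP 9.1.1.4 derives it per participant; only the tabulation is by uropathogen.
- *That participants without a pathogen cannot be classified.* Table 7 classifies them.
- *That ITT is the wrong population for Tables 2.6 and 2.9.* The choice is permitted; the fault is that it is not recorded as a change.

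The planned participant-level clinical outcome summary is free of the repeat-counting problem. These endpoints are exploratory with no hypothesis test, and the primary pharmacokinetic analysis is unaffected.

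**What to change.** - Replace the bullet with a statement that clinical response is taken from the response column of Table 7, one record per participant.
- In the clinical response, clinical cure and therapeutic response tables and plots, count each participant once per uropathogen category and base the Clopper-Pearson intervals on distinct participants.
- Keep isolate-level counting for microbiological outcome and MIC tables, labelled as isolates.
- State the row in which ITT participants without a qualifying uropathogen appear in Tables 2.6 and 2.9.
- List the use of ITT in Tables 2.6 and 2.9 in the SAP 2.1 table of changes, or align both with the protocol's micro-ITT population.

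The cost is SAP wording and display shells. No new data, visits or participants are needed.
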